**TREATMENT**

**DURATION:**

**VRC01:** One day for Dose Groups 1 and 2.

**VRC01:** For Dose Group 3, all have received monthly doses for at least 6 months. Infants who continue to receive breastmilk will receive monthly doses through the complete cessation of breastfeeding up to a maximum of 72 weeks (19 doses).

**VRC01LS:** All infants in Dose Group 4 received a single dose at birth. Infants in Dose Group 4, Cohort 2 will receive a second dose at Week 12 if they have not achieved complete cessation of breastfeeding.

**VRC07-523LS:** All infants in Dose Group 5 will receive a single dose at birth. Infants in Dose Group 5, Cohort 2 will receive a second dose at Week 12 if they have not achieved complete cessation of breastfeeding.

NOTE: It is expected that serum levels will remain detectable for > 1 month after the final dose of VRC01 and at least 6 months after the final dose of VRC01LS or VRC07-523LS.

## STUDY

DURATION: Dose Groups 1 and 2: minimum of 48 weeks  
Dose Group 3: 96 weeks  
Dose Group 4: 96 weeks  
Dose Group 5: 96 weeks

### 2.2 Study Objectives

This Primary SAP addresses the following primary and secondary objectives listed in the study protocol. Other study objectives in the protocol will be addressed in subsequent analysis plans.

#### OBJECTIVES:

Primary: In HIV exposed infants at increased risk for peripartum or breastfeeding HIV transmission:

1. To assess safety of single subcutaneous dose (20 mg/kg or 40 mg/kg) of VRC01 (Dose Groups 1 and 2).
2. To determine pharmacokinetic profile of single dose, subcutaneous VRC01 (Dose Groups 1 and 2). – **This objective will be addressed in a separate PK report.**
3. To assess safety of monthly subcutaneous doses of VRC01 (Dose Group 3).
4. To determine pharmacokinetic profile of monthly subcutaneous doses of VRC01 (Dose Group 3). – **This objective will be addressed in a separate PK report.**
5. To assess safety of one and two subcutaneous doses of VRC01LS (Dose Group 4, Cohorts 1 and 2).
6. To determine pharmacokinetic profile of one and two subcutaneous doses of VRC01LS (Dose Group 4, Cohorts 1 and 2). – **This objective will be addressed in a separate PK report.**
7. To assess safety of one and two subcutaneous doses of VRC07-523LS (Dose Group 5, Cohorts 1 and 2).
8. To determine pharmacokinetic profile of one and two subcutaneous doses of VRC07-523LS (Dose Group 5, Cohorts 1 and 2) – **This objective will be addressed in a separate PK report.**

Secondary:

1. To examine the anti-VRC01 antibody production following immunization.
2. To examine the anti-VRC01LS antibody production following immunization.
3. To examine the anti-VRC07-523LS antibody production following immunization.

The PK objectives will be analyzed and reported in a separate report, created by the study pharmacologist.

### **2.3 Overview of Formal Interim Monitoring**

The study team will monitor the safety of the study participants through calls where adverse events and toxicity reports presenting laboratory and clinical data collected throughout follow-up for the infants enrolled are reviewed. After the first infant enrolled into Dose Group 3 reached the Week 24 milestone, the team began reviews of available safety data of adult and pediatric protocols of VRC01 (from P1112 database and most recent safety reports available from the other protocols) every 6 months. These reviews will continue and include infants in Dose Groups 4 and 5 and data on VRC01LS and VRC07-523LS. In addition, if any of the stopping rules for safety listed in the protocol are met, the study will be reviewed by an independent Study Monitoring Committee (SMC) according to IMPAACT Standard Operation Procedure (SOP) on Study Data and Safety Monitoring.

## **3 Outcome Measures**

### **3.1 Primary Outcome Measures**

Through Day 28 for Dose Groups 1, 2, Cohort 1 in Dose Groups 4 and 5; Week 24 for Dose Group 3; and Week 16 for Cohort 2 in Dose Groups 4 and 5:

- Death
- Grade 3 or higher adverse events
- Vaccine-related Grade 3 or higher adverse events
- HIV infection

Number (%) participants in each category will be summarized for each treatment group.

### **3.2 Secondary Outcome Measures**

From the end of the observation period in the primary outcome measure through the end of follow-up:

- Death
- Grade 3 or higher adverse events
- Vaccine-related Grade 3 or higher adverse events
- HIV infection

Number (%) participants in each category will be summarized for each treatment group.

From vaccine administration to end of follow-up:

- Development of anti-VRC01 antibodies (yes/no)
- Development of anti-VRC01LS antibodies (yes/no)
- Development of anti-VRC07-523LS antibodies (yes/no)

## **4 Analysis principles**

Since the study is not blinded and the dose cohorts will be enrolled sequentially, the data will be presented separately by dose cohort. All subjects who received immunization will be included in the safety and immunology analyses. Exact methods will be used when calculating the 90% CI around proportion estimates of safety data.

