## 8.4 Sample Size and Accrual

Both mothers and infants are enrolled in the study, but only infants receive the VRC01, VRC01LS, or VRC07-523LS immunization(s) and are followed on the study. The study will enroll 79 mother-infant pairs: 13 in each of Dose Groups 1-3 and 10 in each cohort in Dose Groups 4 and 5, with the aim of having 10 evaluable infants in each Dose Group 1-3 and 8 in each cohort in Dose Groups 4 and 5. Evaluable infants must have received the required study immunization(s) and have completed follow-up for the primary safety outcome measure (Day 28 evaluations for Dose Groups 1, 2 and Cohort 1 from Dose Groups 4 and 5; Week 24 evaluations for Dose Group 3; and Week 16 evaluations for Cohort 2 in Dose Groups 4 and 5). This assumes a maximum missing data rate of 23% in Dose Groups 1-3 and 20% in Dose Groups 4 and 5. Non-evaluability could be due to losses to follow-up, missed visits or problems with laboratory samples. Note that infants who do not receive the first immunization will be replaced.

Safety data will be assessed as described in Section 8.5.1. If any of the safety criteria are triggered, enrollment and further immunizations will be temporarily stopped until the SMC reviews the data and advises the protocol team on how to proceed. Section 8.5.1 discusses the error probabilities associated with the safety criteria and Section 8.6.1.2 discusses the precision that the sample size will provide for estimating AE rates and PK success rates. The sample size is based on target precision for the estimation of key safety and PK parameters. The calculations are located in Section 8.6.1.2 for ease of discussion.

We had anticipated that all participants in Dose Groups 1 and 2 would be enrolled within 2 years after Version 1.0 was opened to accrual. In fact, enrollment into both dose groups was more rapid than anticipated: taking less than 9 months to reach full accrual of each dose group. Likewise, Dose Group 3 reached full accrual within approximately 4 months. We had anticipated that Dose Group 4 would be fully enrolled within 1 year of that dose group being opened to accrual. However, this group also reached full accrual much faster than expected, within 6 months. It is anticipated that both cohorts in Dose Group 5 will be enrolled within 1 year after Version 4.0 opens to accrual.

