## 8.6 Analyses

### 8.6.1 Primary Analysis

#### 8.6.1.1 Safety

Each participant's safety data will be summarized as: the worst grade of adverse event experienced during the time period of observation for primary objectives and the worst grade of adverse event judged to be at least possibly related to the immunization(s) during the same time interval. Descriptive analyses will consist of frequency distributions of these safety outcomes, broken down by dose group/Cohort. All available safety data will be used. All infants who receive an initial VRC01, VRC01LS, or VRC07-523LS immunization will be included in all analyses regardless of whether they receive ARV prophylaxis or are HIV-infected.

With the small sample size used in this study, there will be insufficient statistical power for a formal test of differences between dose groups with respect to safety. With insufficient power, a finding of no significant difference would not provide acceptable evidence of no adverse dose effect. Thus, estimates of Grade 3 or higher toxicity rates will be computed separately for each dose group and bounded by 90% confidence intervals (CI), reflecting the precision of the estimates. This will provide 95% assurance that the true rate of severe adverse events is not higher than the upper limits of the CI around the proportion of participants with grade 3 or higher events in the study sample. Because of the small sample sizes and the anticipated low toxicity rates, these intervals will be calculated using exact methods.

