## 8.7 Secondary Analyses

Adverse events occurring after the initial review period and throughout the remainder of follow-up will be summarized in the same way as for the primary safety objective.

The number of infants in each dose group who develop anti-VRC01, VRC01LS, or VRC07-523LS antibodies will be summarized descriptively.

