**The following tables will be restricted to only the participants who received immunization.**

2. Selected characteristics of participants at baseline
  - a. Summary of key characteristics including gender, race, ethnicity, birth weight, age (in days) at randomization, and type of ARV at the time of delivery.
3. Protocol deviations (text)
  - a. Summary of serious protocol deviations reportable per standard IMPAACT policies
4. Study and immunization status (table or text)
  - a. Number receiving immunizations
  - b. Number off study prematurely, by reason and arm
5. Days between randomization and immunization
  - a. Table showing the number of hours between birth and first immunization.
6. Missed or partial visits
  - a. Table showing the number of missed visits and visits conducted remotely due to COVID
7. Primary Safety Outcomes as discussed in Section 3.1  
Through Day 28 for Dose Groups 1, 2, Cohort 1 in Dose Groups 4 and 5; Week 24 for Dose Group 3; and Week 16 for Cohort 2 in Dose Groups 4 and 5:
  - a. Number of deaths
  - b. Number of participants who experienced Grade 3 or higher adverse events
  - c. Number of participants who experienced treatment-related Grade 3 or higher adverse events
  - d. Number of participants who became HIV infected

Number (%) of participants meeting each category, along with exact 90% CI, will be presented.

8. Secondary Safety Outcomes as discussed in Section 3.2

From the end of the observation period in the primary outcome measure through the end of follow-up:

- a. Number of deaths
- b. Number of participants who experienced Grade 3 or higher adverse events
- c. Number of participants who experienced treatment-related Grade 3 or higher adverse events
- d. Number of participants who became HIV infected

Number (%) of participants meeting each category, along with exact 90% CI, will be presented.

9. Table summarizing local reactions at the injection site

10. Anti-VRC01 Antibody Data

- a. The number of infants in each dose group who develop anti-VRC antibodies will be summarized descriptively.

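### Secondary safety is a crude percentage of all immunized infants over windows of 44 to 92 weeks: it reads low whenever infants leave early, and it is not like-for-like between groups whose windows differ.

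*SAP*

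**What the plan says.** **Who is analysed.** SAP 4: "All subjects who received immunization will be included in the safety and immunology analyses". Protocol 8.6.1.1 agrees: "All infants who receive an initial VRC01, VRC01LS, or VRC07-523LS immunization will be included in all analyses". The outcome tables in SAP 5 are restricted by receipt of immunization and by nothing else.

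**Which period.** SAP 3.2 sets the secondary period: "From the end of the observation period in the primary outcome measure through the end of follow-up". It therefore opens where the primary period in SAP 3.1 closes: "Through Day 28 for Dose Groups 1, 2, Cohort 1 in Dose Groups 4 and 5; Week 24 for Dose Group 3". In the two breastfeeding cohorts that point is the Week 16 visit. SAP 2.1 puts the end of follow-up at 48 weeks or later for Dose Groups 1-2 and at 96 weeks for Dose Groups 3-5.

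**Which summary.** SAP 5 item 8: "Number (%) of participants meeting each category, along with exact 90% CI, will be presented". Protocol 8.7 says later adverse events "will be summarized in the same way as for the primary safety objective".

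**What is not stated.** Neither document defines an at-risk set at the start of the secondary window, a rule for infants who leave early, person-time, a time-to-event estimate, or a cumulative safety rate from first dose. SAP 5 items 4 and 6 tabulate premature exits and missed or remote visits but do not connect them to item 8. Table detail is left to the Analysis Implementation Plan (AIP), which is not among the documents.

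**The concern.** A percentage of all immunized infants is a natural summary over a short window with nearly complete observation. The secondary window is long and starts weeks or months after the first dose. An infant lost before it opens can never enter the numerator but remains in the denominator. An infant lost part-way counts the same as one seen to the end. For HIV infection, an infant already infected in the primary period cannot become infected again. The exact interval treats each of these infants as a complete, event-free observation.

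Loss is a realistic prospect. Protocol 1.2 records early concern about retention among women not regularly in care. The Letter of Amendment anticipates missed, remote and out-of-window visits during this period.

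At stake is the late-safety description of each product in a study meant to support dose selection for efficacy trials. Protocol 8.6.1.1 reads the upper confidence limit as 95% assurance that the true severe-event rate is no higher, and Protocol 8.7 carries the method forward. An upper limit that is too low is an error in the unsafe direction.

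**Working it through.** **1. Length of the secondary window** (end of follow-up in SAP 2.1 minus end of the primary period in SAP 3.1)

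| Group | Calculation | Weeks |
|---|---|---|
| Dose Groups 1-2 | 48 - 4 | 44 (minimum) |
| Dose Group 3 | 96 - 24 | 72 |
| Dose Groups 4-5, Cohort 2 | 96 - 16 | 80 |
| Dose Groups 4-5, Cohort 1 | 96 - 4 | 92 |

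**2. Reproducing the plan's interval.** For zero events the exact two-sided 90% upper limit is 1 - 0.05^(1/n). This gives 31.2% for n = 8, 25.9% for n = 10 and 20.6% for n = 13, matching the 31%, 26% and 21% in Protocol Table 7. Of the 15 rows in that table, 14 agree to rounding. The exception is 1/10, where the upper limit computes to 39.4% against a printed 40%.

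**3. Loss before the window.** Compare x/N (all immunized) with x/(N - g), where g infants have gone. The documents give no value for g, so it is an assumption; N is the planned size.

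| N | g | Events | All immunized, % (90% CI) | At risk, % (90% CI) |
|---|---|---|---|---|
| 10 | 2 | 0 | 0 (0-25.9) | 0 (0-31.2) |
| 10 | 2 | 1 | 10.0 (0.5-39.4) | 12.5 (0.6-47.1) |
| 10 | 2 | 2 | 20.0 (3.7-50.7) | 25.0 (4.6-60.0) |
| 13 | 3 | 0 | 0 (0-20.6) | 0 (0-25.9) |
| 13 | 3 | 2 | 15.4 (2.8-41.0) | 20.0 (3.7-50.7) |

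With N = 10 and two events, the at-risk percentage is 20.0, 22.2, 25.0, 28.6 and 33.3 for g = 0, 1, 2, 3 and 4. At g = 0 nothing changes. For HIV, one infant of 10 already infected and no later infections moves the upper limit from 25.9% to 28.3%.

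**4. Effect on the 95% assurance.** Suppose 8 of 10 infants are observed and the true risk is 30%. On a denominator of 10, the zero-event limit of 25.9% misses the truth, which happens with probability 0.7^8 = 0.058, so coverage is 94.2%. On a denominator of 8 the zero-event limit is 31.2% and coverage is 100%. With all 10 observed it is 1 - 0.7^10 = 97.2%.

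**5. Loss during the window.** Assume a constant event rate giving 20% over 92 weeks, so λ = -ln 0.8 = 0.223 per window, and a constant exit rate θ. The expected crude percentage is λ/(λ + θ) × [1 - exp(-(λ + θ))]. With 20% leaving by the end, θ = λ and this is 0.5 × (1 - 0.64) = 18.0%. If the same 20% leave before the window opens, it is 0.80 × 20.0 = 16.0%.

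**6. Window length alone, no loss.** At that same event rate, the expected percentage over w weeks is 1 - 0.8^(w/92): 10.1% at 44 weeks, 16.0% at 72, 17.6% at 80 and 20.0% at 92. Identical underlying risk appears as a twofold difference between Dose Groups 1-2 and Cohort 1 of Dose Groups 4-5.

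**The case against.** Several counter-arguments have force.

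- **Loss is not established.** Protocol 8.4 states: "This assumes a maximum missing data rate of 23% in Dose Groups 1-3 and 20% in Dose Groups 4 and 5". A reader might infer that a fifth of infants will have left before the window opens, so that the rates must be wrong. The text does not support that. The figure is a ceiling on non-evaluability for the primary outcome; it also covers visits not attended and unusable samples, and such infants can remain in follow-up. For Dose Group 3, the treatment-duration text in both documents describes every infant as having had monthly dosing for six months or longer, which suggests little loss before Week 24.
- **Early deaths.** A reader might infer that counting infants who died in the primary period is an error. It is a defensible definition: the death is reported in that period, and an all-immunized proportion is a cumulative risk with death as a competing event. The bias argument rests on infants lost, and on infants already infected for the HIV outcome.
- **Comparison between groups.** A reader might infer that no cohorts can be set side by side. Dose Groups 1 and 2 share a protocol window, as do the matching cohorts of Dose Groups 4 and 5. No between-group safety test is planned.
- **The AIP may define the denominator**, and premature exits will be visible from SAP 5 item 4.
- **The intervals are already wide.** One or two infants move the estimate by much less than the interval's width.

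The first three narrow the point. The fourth does not remove it: SAP 4 states the governing set, so a different AIP denominator would have to be reconciled with it, and listing exits elsewhere does not correct the percentage in item 8. The last bears on priority, not on whether the denominator is right.

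**Conclusion.** As written, the secondary summary uses a denominator that takes no account of time at risk. Whenever infants leave before or during the window, or are already infected for the HIV outcome, the percentage and its upper limit are too low as estimates of risk over the full window. If nobody leaves, there is no bias from loss.

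The size is illustrative: with 2 of 10 gone before the window, the zero-event upper limit is understated by 5.3 points (31.2 - 25.9), and two events read 5 points low. This assumes that loss is unrelated to event risk and that infants who leave have no later events recorded. That they would be tabulated as event-free is inferred from the all-immunized rule; the documents do not say so outright.

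Unequal windows are a separate limitation that needs no loss assumption. They affect only groups with different windows, and they affect side-by-side reading, not a planned test. The point concerns a descriptive secondary analysis and is a worthwhile, inexpensive improvement.

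**What to change.** In SAP 5 item 8, with a matching sentence in SAP 4:

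- Show for each cohort the number alive and in follow-up at the start of the secondary window, and use it as the denominator for the percentage and exact 90% CI. For HIV infection, also require that the infant is not yet infected.
- Because that corrects only loss before the window, add first events per infant-year at risk with an exact 90% Poisson interval, and/or cumulative incidence from first dose to a common Week 48, plus Week 96 for Dose Groups 3-5. Treat death as a competing event for non-fatal outcomes; a Kaplan-Meier estimate that censors deaths would overstate their risk.
- Keep the crude counts on all immunized infants beside these, and align the AIP.

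The cost is a SAP clarification and a short program. Protocol 6.1 already collects Grade 3 or higher events throughout the study, and premature exits are already tabulated, so no new event collection is needed. The drawbacks are slightly more analysis and wider intervals. Cumulative-incidence intervals are approximate at about 10 infants per cohort, which is why the exact Poisson rate is offered.

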## 5 Report Contents

Detailed descriptions of the content of each of the following sections are given in the AIP.

1. Accrual
  - a. Table with number enrolled
  - b. Table with enrollment by month
  - c. Table with enrollment by site

**The following tables will be restricted to only the participants who received immunization.**

2. Selected characteristics of participants at baseline
  - a. Summary of key characteristics including gender, race, ethnicity, birth weight, age (in days) at randomization, and type of ARV at the time of delivery.
3. Protocol deviations (text)
  - a. Summary of serious protocol deviations reportable per standard IMPAACT policies
4. Study and immunization status (table or text)
  - a. Number receiving immunizations
  - b. Number off study prematurely, by reason and arm
5. Days between randomization and immunization
  - a. Table showing the number of hours between birth and first immunization.
6. Missed or partial visits
  - a. Table showing the number of missed visits and visits conducted remotely due to COVID
7. Primary Safety Outcomes as discussed in Section 3.1  
Through Day 28 for Dose Groups 1, 2, Cohort 1 in Dose Groups 4 and 5; Week 24 for Dose Group 3; and Week 16 for Cohort 2 in Dose Groups 4 and 5:
  - a. Number of deaths
  - b. Number of participants who experienced Grade 3 or higher adverse events
  - c. Number of participants who experienced treatment-related Grade 3 or higher adverse events
  - d. Number of participants who became HIV infected

Number (%) of participants meeting each category, along with exact 90% CI, will be presented.

8. Secondary Safety Outcomes as discussed in Section 3.2

From the end of the observation period in the primary outcome measure through the end of follow-up:

- a. Number of deaths
- b. Number of participants who experienced Grade 3 or higher adverse events
- c. Number of participants who experienced treatment-related Grade 3 or higher adverse events
- d. Number of participants who became HIV infected

Number (%) of participants meeting each category, along with exact 90% CI, will be presented.

9. Table summarizing local reactions at the injection site

10. Anti-VRC01 Antibody Data

- a. The number of infants in each dose group who develop anti-VRC antibodies will be summarized descriptively.

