Single and multiple dose pharmacokinetic data from the present study will be used to select a dose regimen for repeated dosing that will be needed for protection during ongoing breast milk exposure. Protective efficacy will be determined in a future study which cannot begin until the present study determines a safe dose that provides a sufficient trough level. Demonstration that a neutralizing antibody prevents HIV transmission in humans would be a major milestone in the field of HIV prevention. Although ample data in animal models demonstrate protection with neutralizing antibody, this has yet to be studied in humans. Demonstration of efficacy will lead toward further development of mAb for use in prevention of MTCT and potentially for other post-exposure prophylaxis. It will also provide proof-of-concept for neutralizing antibody protection that will be important for design of active vaccines to induce immunity.

While VRC01LS is a very promising product with excellent breadth, potency and a very long half-life, the newer product VRC07-523LS has increased potency and increased breadth compared with either VRC01 product. Thus, if VRC07-523LS has a similar safety profile and a half-life that approaches that of VRC01LS, then it would be the preferred product to take into subsequent trials.

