## **6 PARTICIPANT MANAGEMENT**

### **6.1 Toxicity Management**

The DAIDS Table for Grading the Severity of Adult and Pediatric Adverse Events, (DAIDS AE Grading Table), Corrected Version 2.1, July 2017, must be used and is available on the RSC website at <https://rsc.niaid.nih.gov/clinical-research-sites/daims-adverse-event-grading-tables>

Management of adverse experiences is done according to the best clinical practice and the judgment of the site investigator. Alternate explanations for clinical and laboratory abnormalities must be sought. Laboratory normals will be the institutional values. However, if a site does not have an age-specific normal range/value for a particular lab, the site should use the latest edition of the Harriet Lane Handbook for normal ranges/values and document this for

monitoring purposes. Abnormal clinical and laboratory findings should be followed until resolution to < Grade 2, or no further change expected.

This study involves a single or multiple dose(s) of VRC01, VRC01LS, or VRC07-523LS antibody. Safety data will be collected and reviewed by the study team on regular (twice a month) study conference calls.

Sites record and submit CRFs to the Data Management Center on all AEs from the time of the initial immunization as follows:

For Dose Groups 4 and 5 (both cohorts), all laboratory events required by the Schedules of Evaluations should be recorded on CRFs regardless of grade. See the CRF instructions for further details. For all other events:

- For Grade 1 reactogenicity AEs, and all Grade 2 AEs that study sites assess as possibly, probably or definitely related to the study product, and all AEs grade 3 or higher (regardless of their relationship to study product): CRFs should be submitted through the entire course of study.
- For all Grade 1 AEs (other than reactogenicity AEs), and Grade 2 AEs that sites assess as definitely not or probably not related to the study product: CRFs should only be submitted for these AEs occurring up to 30 days after the single immunization for Dose Groups 1 and 2 and Dose Groups 4 and 5 (Cohort 1) or 30 days after the final immunization for Dose Group 3 and Dose Groups 4 and 5 (Cohort 2). After that, sites will not be required to record/submit these AEs on CRFs. Note that sites should continue to report – beyond the time periods specified above – unresolved AEs that began during the reporting period.

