### 8.2.1 Primary Outcome Measures

#### 8.2.1.1 Safety

Through Day 28 for Dose Groups 1, 2, Cohort 1 in Dose Groups 4 and 5; Week 24 for Dose Group 3; and Week 16 for Cohort 2 in Dose Groups 4 and 5:

- Death
- Grade 3 or higher adverse events
- Vaccine-related Grade 3 or higher adverse events
- HIV infection

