## APPENDIX IE: Schedule of Evaluations (Dose Group 4, Cohort 1: non-breastfeeding)

	Screen 	Entry/Day 0  0 Hour	Day 1/24 hr  ± 6 hr	Day 14 +/-3 days	Day 28 +/-3 days	Wk 8 +/-1 wks	Wk 12; +/-1 wk	Wk 24 +/- 1 wk	Wk 36 +/- 1 wk	Wks 48, 60, 72, 84 +/- 2 wk	Wk 96: End of Study +/- 2 wk	Early Study D/C 
History 	X	X	X	X	X	X	X	X	X	X	X	X
PE 	X	X	X	X	X	X	X	X	X	X	X	X
VRC01LS 		X										
LABORATORY EVALUATIONS												
Hematology 	0-1mL			1mL	1mL		1mL	1mL				1mL
Chemistries 	1mL			1mL	1mL		1mL	1mL				1mL
HIV-1 NAT 	1mL 			1mL	1mL		1mL	1mL	1mL			1mL
HIV Ab test 										2mL	2mL	2mL
Lymphocyte: CD3/CD4/CD8 	1mL											1mL
VRC01LS Plasma levels 		2mL	1mL	1-2mL 	2mL	2mL	2mL	2mL	2mL	2mL	2mL	2mL
PBMC 		X	X	X	X	X	X	X	X	X	X	X
VRC01LS serum 		0-1mL		0-1mL 	0-1mL	0-1mL	2mL	2mL	2mL	2mL	2mL	2mL
Anti-VRC01LS Ab 		X				X	X	X	X	X	X	X
Oral secretions 		X	X	X	X	X	X	X	X	X	X	X
Total Blood Volume Infant (mL) 	3-4mL	2-3mL	1mL	4-6mL	5-6mL	2-3mL	7mL	7mL	5mL	6mL	6mL	10mL
	NOTE: 17-23mL from birth to 8 weeks 											

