## APPENDIX IG: Schedule of Evaluations (Dose Group 5, Cohort 1: non-breastfeeding)

	Screen 		Entry/Day 0  0 Hour		Day 1/24 hrs  ± 6 hrs	Day 3 ± 1 day	Day 7 +/-3 days	Day 14 +/-3 days	Day 28 +/-3 days	Wk 8 +/-1 wks		Wk 12; +/-1 wk	Wk 24 +/-1 wk	Wks 48, 60, 72, 84 +/-2 wk	Wk 96: End of Study +/- 2 wk	Early Study D/C 
History 	X	X	X	X	X	X	X	X	X	X	X	X	X	X	X	X
PE 	X	X	X	X	X	X	X	X	X	X	X	X	X	X	X	X
VRC07-523LS 		X														
LABORATORY EVALUATIONS																
Hematology 	0-1mL							1mL		1mL	1mL					1mL
Chemistries 	1mL							1mL		1mL	1mL					1mL
HIV-1 NAT 	1mL 					1mL	1mL			1mL	1mL					1mL
HIV Ab test 														2mL	2mL	2mL
VRC07-523LS plasma levels 		2-3mL 	1mL	1mL	1mL	2mL	2mL	3mL	3mL	3mL	3mL	3mL	3mL	3mL	3mL	3mL
PBMC 		X	X			X	X	X	X	X	X	X	X	X	X	X
VRC07-523LS serum 		0-1mL 				0-1mL 	0-1mL 	0-1mL 	2mL	2mL	2mL	2mL	2mL	2mL	2mL	2mL
Anti-VRC07-523LS Ab 		X							X	X	X	X	X	X	X	X
Oral secretions 		X	X		X	X	X	X	X	X	X	X	X	X	X	X
Total blood volume infant (mL) 	2-3mL	2-4mL	1mL	1mL	1mL	3-4mL	5-6mL	3-4mL	8mL	8mL	6mL	7mL	7mL	10mL		
	NOTE: 18-24mL from birth to 8 weeks 															

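### Dose Group 5 has one fewer scheduled safety-laboratory draw than Dose Group 4 but two more early clinical visits, so the combined Grade 3+ rate is not ascertained equally for the two products

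*SAP*

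**What the plan says.** The primary safety outcome in SAP section 3.1 and section 5, item 7(b), is the "Number of participants who experienced Grade 3 or higher adverse events", shown by group as number, percentage and exact 90% interval. Item 7(c) repeats the count for treatment-related events. The windows run through Day 28 for Dose Groups 1 and 2 and for Cohort 1 of Dose Groups 4 and 5, then "Week 24 for Dose Group 3; and Week 16 for Cohort 2 in Dose Groups 4 and 5" (Protocol 8.2.1.1). Under Protocol 8.6.1.1 each infant is scored by "the worst grade of adverse event experienced during the time period of observation for primary objectives", and the rates are computed separately by dose group, "bounded by 90% confidence intervals (CI), reflecting the precision of the estimates".

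Laboratory results feed this count. For Dose Groups 4 and 5, Protocol 6.1 says "all laboratory events required by the Schedules of Evaluations should be recorded on CRFs regardless of grade", and Grade 3 or higher events are reported throughout the study. Protocol 8.5.1 describes Grade 3 neutropenia and anemia as common in infants on ARVs, and hyperbilirubinemia as common in the first weeks of life. It leaves them out of the stopping rule. No such exclusion is stated for the primary outcome.

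On how the products will be weighed, Protocol 1.2 says that "if VRC07-523LS has a similar safety profile and a half-life that approaches that of VRC01LS, then it would be the preferred product" for later trials.

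**The concern.** A worst-grade-per-infant outcome depends on how often each infant is looked at. Each extra CBC or chemistry panel is another chance to catch a transient Grade 3 value, and each extra visit is another chance to record a clinical event. The visit schedule changed between Dose Group 4 and Dose Group 5 in both respects. If the two Grade 3+ rates are set beside each other to judge whether the safety profiles are similar, part of any difference, or part of an apparent similarity, could come from the schedule and not from the product. The exact intervals describe sampling error only and would not show this.

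**Working it through.** **1. The plan's own figures.** With no events, the exact 90% upper limit is 1 − 0.05^(1/n). This gives 31.2% for 0/8, 25.9% for 0/10 and 20.6% for 0/13, against 31%, 26% and 21% in Protocol Table 7. The intervals are right, but they take the ascertainment as given.

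**2. Scheduled post-dose CBC/chemistry in the primary window** (Protocol Appendices IE to IH):

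| | Dose Group 4 | Dose Group 5 |
|---|---|---|
| Cohort 1, through Day 28 | Days 14, 28 (2 draws) | Day 28 (1 draw) |
| Cohort 2, through Week 16 | Days 14, 28, Weeks 12, 14 (4 draws) | Day 28, Weeks 12, 14 (3 draws) |
| Clinical visits, Days 1 to 28 | Days 1, 14, 28 | Days 1, 3, 7, 14, 28 |

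Week 14 sampling is described for infants who receive a second dose (Protocol 9.2 and the column headings of Appendices IF and IH). Without a second dose the Cohort 2 counts are 3 and 2, so the gap is still one draw.

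**3. Check against the total-volume rows.** The Appendix IG table is misaligned in the text available, so component volumes were added up:
- Dose Group 4, Day 14: CBC 1 + chemistry 1 + NAT 1 + plasma 1–2 + serum 0–1 = 4–6 mL, as stated.
- Dose Group 5, Day 14: NAT 1 + plasma 2 + serum 0–1 = 3–4 mL, as stated. CBC and chemistry would bring it to 5–6 mL.
- Dose Group 5, Day 28: CBC 1 + chemistry 1 + NAT 1 + plasma 2 + serum 0–1 = 5–6 mL, as stated.
- Week 14, both groups: CBC 1 + chemistry 1 + plasma 2 + serum 2 = 6 mL, as stated.
- Week 16, both groups: plasma 2 + serum 2 = 4 mL, as stated, which leaves no CBC or chemistry.

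**4. Illustration for laboratory events only.** The documents give no per-draw rate. Assume the same rate p for both products and independent draws. The expected share of infants with at least one Grade 3+ laboratory result in k draws is 1 − (1 − p)^k.

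| p per draw | Cohort 1: DG4 (k=2) vs DG5 (k=1) | Cohort 2: DG4 (k=4) vs DG5 (k=3) |
|---|---|---|
| 5% | 9.8% vs 5.0% | 18.5% vs 14.3% |
| 10% | 19.0% vs 10.0% | 34.4% vs 27.1% |
| 15% | 27.8% vs 15.0% | 47.8% vs 38.6% |

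With 10 infants in each Cohort 1 and p = 10%, the expected counts are 10 × 0.19 = 1.9 and 10 × 0.10 = 1.0. Dose Group 4 then shows the higher count with probability 0.60 and Dose Group 5 with probability 0.18, although the true rates are equal. If every abnormality present at Day 14 is still present at Day 28, the gap is zero.

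**5. Dilution in the combined outcome.** Add an assumed independent clinical Grade 3+ rate c, equal in both groups, with p = 10% in Cohort 1. At c = 10% the combined rates are 1 − 0.90 × 0.81 = 27.1% and 1 − 0.90 × 0.90 = 19.0%. At c = 30% they are 1 − 0.70 × 0.81 = 43.3% and 1 − 0.70 × 0.90 = 37.0%. The ratio falls from 1.9 for laboratory events alone to 1.4 and then 1.2.

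**The case against.** The strongest reply is that the plan makes no such comparison. Protocol 8.6.1.1 disclaims a formal test between dose groups, SAP section 4 presents the data separately by dose cohort, and the sentence in Protocol 1.2 is rationale with no endpoint or threshold attached. This stands: the Grade 3+ rates are not a formal selection rule. What remains is that safety similarity is a stated condition for preferring VRC07-523LS, and these separate rates are what readers will use to judge it.

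Second, Dose Group 5 adds visits at Days 3 and 7 with history, a targeted examination and diary-card review (Appendices IG and IH), where Dose Group 4 has a caregiver contact at 3 to 5 days. That can raise clinical detection for VRC07-523LS. This also stands. A reader might infer from the dropped draw that the schedule biases the comparison towards VRC07-523LS. The documents support that for laboratory events only, and the net direction for the combined outcome is unknown.

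Third, item 7(c) counts treatment-related events, and background laboratory abnormalities are less likely to be judged related. This limits the concern for 7(c) but not for 7(b).

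Fourth, the 10-infant cohorts carry wide intervals: Table 7 gives 0.5% to 40% for 1/10, against a Cohort 1 gap of 0.9 expected infants at p = 10%. True, but imprecision does not make a known difference in ascertainment less worth showing.

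Fifth, table detail sits in the Analysis Implementation Plan, which is not among the documents. It may already contain a split. The SAP does not call for one.

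**Conclusion.** The concern holds in a limited form. Between Dose Groups 4 and 5 there is a one-draw difference in scheduled safety laboratories in each cohort, and a two-visit difference the other way in early clinical contact. The combined Grade 3+ rate is therefore not like for like across the two products. The laboratory part favours VRC07-523LS by an amount between nil (abnormalities persist between draws) and the figures in the table above, which rest on assumed per-draw rates and independence.

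Two larger readings are tempting and should not be made. One is that the reported Grade 3+ rate could be about doubled in Dose Group 4. That ratio applies only to Cohort 1 laboratory events under independence; the Cohort 2 ratio at p = 10% is 34.4/27.1 = 1.27, and clinical events dilute both. The other is to point to the spread across all groups, from one post-dose CBC in Dose Groups 1 and 2 to six in Dose Group 3. That mixes a 28-day with a 24-week window and overlooks that Dose Groups 1 and 2 have two chemistry panels (Days 7 and 14). Dose Group 3 also has no part in the comparison of VRC07-523LS with VRC01LS.

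The Week 16 window for Cohort 2 is not mislabelled. It is an adverse-event window that ends with a history and examination. It only needs a note that the last scheduled safety laboratories fall earlier.

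**What to change.** Keep SAP section 3.1 and item 7(b)–(c) as the primary outcome, and add supportive rows:
- Split Grade 3+ events into clinical and scheduled-laboratory events. State which row takes results from unscheduled draws, and that an infant can appear in both rows.
- For laboratory events, show Dose Groups 4 and 5 at shared visits only: Day 28 in Cohort 1; Day 28, Week 12 and, where drawn, Week 14 in Cohort 2. Give the number of infants with a result at each visit.
- Put Dose Group 4 Day 14 on its own line.
- Footnote that the last scheduled Cohort 2 safety-laboratory draw in the primary window is Week 14.

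The cost is a few more rows with small counts in the SAP and the Analysis Implementation Plan. No new samples or visits are needed. If the Analysis Implementation Plan already has the split, a sentence in the SAP pointing to it is enough, provided the shared-visit rows are there too.
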